9.4.10 Transition of Subjects on MDI Therapy To/From Pump Therapy

To assist subjects who enter the study on MDI therapy, investigators and their staff will be instructed on best practices regarding the safe transition from MDI therapy to pump use at the start of the study and a safe transition back to MDI therapy at the end of the study.

For subjects transitioning from MDI to Pump:

- Consider reducing MDI total daily dose by 25% to calculate pump total daily dose before calculating pump settings
- Consider instructing subjects not to administer their long-acting insulin dose the night before/morning of the scheduled pump start.
 - If pump therapy is initiated within 24-36 hours of the last long-acting insulin injection (depending on the duration of action of the brand administered), consider setting a temporary basal rate of 0% to run until that time has passed

For subjects transitioning back to MDI therapy after study participation ends:

- Consider recalculating injection doses based on pump settings, or returning to that subject's previous MDI dose schedule and adjust as needed

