9.8 Subject Exit, Withdrawal or Discontinuation

Subjects may choose to withdraw from the study at any time by notifying investigational center staff of their intent.

If a subject chooses to end his or her study participation or if the subject is removed from the study at the Investigator's discretion or for failure to meet the study requirements, the reason for

withdrawal must be documented. All study devices and supplies must be returned (as applicable) and documented both in source documents and on an eCRF. Following study exit, subjects will receive standard medical care from their own providers.

A subject will be withdrawn from the study if:

- In the opinion of the investigator, the subject's health or safety would be compromised by continuing in the study (e.g., infection at skin site, severe skin reaction to adhesive).
- In the opinion of the investigator, it is in the subject's best interest to discontinue participation in the study.
- During the course of the study, subject begins using hydroxyurea.
- During the course of the study, subject uses insulin that is not allowed to be used in the study. The only permitted insulins are Humalog, Novolog/NovoRapid and Admelog.
- During the course of the study, subject begins participation in another investigational study (drug or device).
- At the discretion of the investigator: during the study it becomes known that subjects are repeatedly using a non-linked BG meter for SMBG or a system that replaces SMBG.
- During the course of the study, subject begins abusing illicit drugs.
- During the course of the study, subject begins abusing marijuana.
- During the course of the study, subject begins abusing prescription drugs.
- During the course of the study, subject begins abusing alcohol.
- During the course of the study, subject receives red blood cell transfusion or erythropoietin.
- During the course of the study, the subject demonstrates that he/she is not able to comprehend instructions for study procedures, as evaluated by the appropriate research staff.
- During the run-in period, a subject repeatedly activates SmartGuard feature when instructed otherwise, e.g., SmartGuard feature is turned on (as applicable at the discretion of the investigator).
- During the course of the study, subject is taking oral, injectable, or IV glucocorticoids. (Note: Intra-articular injections to treat pain (e.g., joint pain, bursitis, etc.) are permitted.)

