 - Exception: During the continued access period in Phase 1 of the study, subjects will be allowed to receive orally administered steroid treatments for a maximum of 2 weeks. Intra-articular injections to treat pain (e.g., joint pain, bursitis, etc.) continue to be permitted. Duration of use as well as type of steroid used must be documented on the Concomitant Medications CRF.
- During the study, (female) subject becomes pregnant.
- During the study, the subject experiences one severe hypoglycemic episode, if it is related to the use of MiniMed 780G system SmartGuard feature.
- During the study, the subject experiences one episode of DKA or HHS, if it is related to the use of MiniMed 780G system SmartGuard feature.
- During the study, subject has a cardiovascular event or any vascular event such as stroke.

Documentation of the reason(s) leading to subject withdrawal will be kept in the subject's source documentation.

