11.3 Reporting of Adverse Events

The investigator or designee will record ALL AEs while the subject is enrolled in the clinical study. Each AE needs to be assessed for its device or procedure relatedness. A device related AE is associated with the use of the study devices (e.g., infection of sensor site or infusion set occlusion resulting in DKA). A procedure related AE is associated with testing related to the study procedures specified in the CIP (e.g., needle (blood draw) insertion pain).

Examples of device or procedure related AEs include:

- **Device** related (ADE): insertion site infection
- Serious adverse **device effect**: cellulitis at device insertion site requiring hospitalization
- **Procedure** related AE: bruising at needle (blood draw) insertion site

Subjects participating in the study have diabetes and are expected to experience hypoglycemia and or hyperglycemia. These normal events are not expected to be reported to sponsor as this is not considered an untoward event, but rather an expected occurrence. Any glycemic excursion that meets the protocol definition of severe hypoglycemia, severe hyperglycemia, HHS, or DKA is considered an untoward event and a worsening from the subject's baseline and would be reported to sponsor on an AE eCRF.

Baseline medical conditions should only be reported to sponsor on an AE eCRF if there is a worsening from the subject's baseline. For example, a subject previously diagnosed with asthma is hospitalized for severe asthma attack would be a reportable event.

Adverse events will be documented in the subject source file and reported to sponsor on an eCRF. The investigational center is responsible for documentation of AEs including obtaining source documents related to the event, such as emergency medical technician/paramedic reports, hospital records (admission summary; lab results, test results, discharge summary) or device uploads to support the event. Source documents will be reviewed to determine if additional AEs have occurred and require reporting.

Adverse events that have not resolved at the time of the subject's discontinuation or completion of the study should have an "outcome" of Not Recovered/Not Resolved at study end in subject source and on an eCRF. The investigator should ensure that subject is aware of any follow-up or additional treatment that is required for any ongoing AE at EOS participation; however, there will be no eCRF entry for the ongoing follow-up.

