12.1 Clinical Events Committee

A clinical events committee (CEC) consisting of external physicians with an expertise in endocrinology and the management of diabetes including insulin pumps and CGM will be convened. The CEC will review AEs as required per protocol, which include reports of:

- Serious adverse event
- Serious adverse device effect
- Unanticipated adverse device effect
- Severe hypoglycemia
- Diabetic ketoacidosis
- Diabetic hyperglycemic hyperosmolar syndrome
- Severe hyperglycemia

CEC is to review and adjudicate unanticipated adverse device effects (UADE), device related DKA, device related HHS, and device related severe hypoglycemia within 10 business days from the time that the sponsor is notified. Adjudication will occur once all applicable documentation has been

received and reviewed by the CEC.

The CEC will assess events to determine agreement or disagreement with the investigator classification of an event.

If the CEC disagrees with the investigator's classification of the event, the rationale will be provided to the investigator. If the investigator agrees with the CEC's adjudication, the CRF documenting the AE will be updated accordingly.

If the investigator does not agree with the CEC's adjudication classification, both determinations will be provided within the final report; however, the CEC's adjudication will be used for data analysis. The disagreement will also be included in reporting to IRBs and regulatory authorities, if required.

The CEC may review applicable information for device related AEs which may include:

- Whether or not the event was unanticipated
- Review of sensor data from CareLink Personal/CareLink system software report (when applicable)
- Review of pump data from CareLink Personal/CareLink system software report (when applicable)
- Misuse of the device by the user

Review of events may require the following information. Final disposition may be delayed based on obtaining this information:

- Monitoring by sponsor at investigational center
- Device return and failure analysis
- CareLink Personal/CareLink system software upload and review of software reports
- Subject clarification to investigational center regarding details about the event
- Source documents that support event: Paramedic records; ER records; Lab records; Hospital admission and discharge summary

The following factors should be carefully considered in the CEC's recommendation to sponsor:

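### Events that force withdrawal under Protocol 9.8 have no defined outcome follow-up after exit, because 11.3 ends eCRF follow-up there, so later deaths, permanent impairment and fetal outcomes may be missed

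*Protocol*

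**What the plan says.** **Withdrawal.** Protocol 9.8 opens its list with "A subject will be withdrawn from the study if". Four of the entries matter here:

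- "During the study, subject has a cardiovascular event or any vascular event such as stroke" (no relatedness condition);
- a single episode of severe hypoglycemia, where SmartGuard use is judged to be the cause;
- on the ketoacidosis and hyperosmolar side, "During the study, the subject experiences one episode of DKA or HHS, if it is related to the use of MiniMed 780G system SmartGuard feature";
- pregnancy.

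The section does not say how soon after the event the subject must exit. It hands care after exit to the subject's own providers.

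**Adverse event recording.** Protocol 11.3 states: "The investigator or designee will record ALL AEs while the subject is enrolled in the clinical study". An event unresolved at discontinuation or completion receives the outcome code Not Recovered/Not Resolved in source and eCRF. The investigator must make sure the subject knows what further care is needed; "however, there will be no eCRF entry for the ongoing follow-up".

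**What counts as serious.** The definition in Protocol 11.2 includes death, permanent impairment, fetal distress, fetal death and congenital abnormality.

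**Reporting.** SAP 7.1.1 draws the trial data from eCRFs, questionnaires and device uploads. SAP 7.3.1.8 lists the safety summaries: SAEs, SADEs, UADEs, and incidence of severe hypoglycemia, severe hyperglycemia, DKA and HHS.

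**The concern.** Either rule alone could be defended. Withdrawing a subject after a grave event protects that subject, and closing routine adverse event collection at exit is a common economy. Together they mean that some of the gravest events end participation, and the end of participation then stops planned follow-up of how those events turn out.

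The protocol classes this as a significant-risk device study (10.5), and it is meant to support a labeling expansion. Readers of the safety tables will want to know whether a stroke or a device-related DKA ended in recovery, disability or death. If the trial follows its own text exactly, a death soon after exit can sit in the database as an unresolved event. Any such loss would fall among the serious events rather than at random.

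**Working it through.** No arithmetic applies. The check is whether the two sections interact as described, and whether any other passage closes the gap.

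**1. Does withdrawal meet the recording rule?** Yes. Section 9.8 makes withdrawal mandatory for the four triggers. The rule in 11.3 covers events unresolved at discontinuation as well as at completion. A subject withdrawn with the event still open falls under both.

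**2. What happens to a later outcome?** Take a subject who has a stroke, is withdrawn while it is unresolved, and dies afterwards; the order is assumed for illustration. If the death is treated as the course of the open event, 11.3 excludes an eCRF entry for it. If it is treated as a new event, it falls outside the enrollment window. On either reading, no rule in 11.3 requires the death to be entered.

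**3. Pregnancy.** Fetal death and congenital abnormality are serious under 11.2, yet pregnancy ends participation. The schedule of events has a pregnancy test at Visit 1 only, and neither document describes follow-up to pregnancy outcome. A fetal outcome arising after exit has no stated place to be recorded.

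**4. Does another passage supply follow-up?** These are the candidates:

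- *Early-exit visit (9.1, note to Table 3).* Exit during the study period triggers the Visit 18 requirements, including the adverse event question. It is asked once, at exit.
- *Prompt reporting (11.4).* Serious events and the named glycemic events are to be reported quickly. This secures the index event, not its end.
- *Source records (11.3, 12.1).* Sites obtain hospital records and discharge summaries and review them for further reportable events. The Clinical Events Committee (CEC) can wait for such records: "Final disposition may be delayed based on obtaining this information". This can reveal a death or disability during the index admission. It does not reach beyond the records obtained.
- *CEC adjudication (12.1).* If the investigator accepts a CEC reclassification, the form is updated. That corrects classification; it does not require the final outcome.
- *FDA updates (12.2).* The sponsor passes on information as it becomes available, but only for UADEs and device-related DKA, HHS and severe hypoglycemia. These updates go to the agency, not to the study database.
- *UADE reports (11.5).* The clock runs from investigator awareness and is not tied to enrollment. It covers UADEs only, and nothing requires the investigator to go looking.
- *Site suspension or termination (16.10.2).* Observations are to be completed at the time of termination, with care then passing to the subject's own providers.

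**5. Result.** None of these routes requires the site to obtain or enter the final outcome of an event open at exit. A cardiovascular event that is not a UADE is the least covered, with only the SAE report and the CEC source-document route.

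**The case against.** The strongest reply is that the plan keeps more open than 11.3 alone suggests, and much of it stands. A reader might infer any of the following; the documents do not support them.

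- *Exit is immediate.* Section 9.8 gives no timing. For severe hypoglycemia, DKA and HHS, relatedness to SmartGuard must be judged first. Anything that happens before exit, including death, is recorded, and events that resolve before exit are unaffected.
- *Later outcomes are never recorded, or the eCRF is closed.* Section 12.1 provides for a form update after CEC adjudication, and discharge records are reviewed for additional events. Section 11.3 excludes entries for ongoing follow-up; it does not lock the form.
- *The gap is the committees' review time.* The CEC and DMC steps are 10 business days each, 20 together. They apply only to UADEs and device-related DKA, HHS and severe hypoglycemia, can run longer while documents are awaited, and start from sponsor notification rather than exit. They do not measure lost follow-up.
- *Serious events are systematically undercounted.* An event already reported as an SAE stays counted whatever follows. The DMC's routine event rates and the SAP's incidence figures depend mainly on that count. What can be lost is outcome, later seriousness and sequelae.
- *Every exiting subject needs a further safety contact.* Section 9.4.10 does place the return to injections outside participation ("For subjects transitioning back to MDI therapy after study participation ends"), but it offers considerations for the transition and does not imply that event collection continues.

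The objection does not remove the central point. The partial routes depend on what happens to be in the records or to reach the investigator, and no passage asks for the outcome.

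**Conclusion.** The concern holds in a limited form. Withdrawal is mandatory for these events, follow-up of events open at exit is kept out of the eCRF, and no post-exit safety rule appears elsewhere in the protocol or SAP. Later outcomes, including death, permanent impairment and fetal outcomes, are therefore not systematically captured and may be absent from the safety summaries.

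The size cannot be stated. The documents give no rate for the triggering events, no interval from event to exit, and no proportion unresolved at exit. For the triggers discussed, the affected group is subjects withdrawn with the event still open, plus pregnancies; it is probably small but includes some of the events of greatest safety interest. SAEs still open at normal completion face the same rule. The HbA1c and time-in-range tests do not use adverse event outcomes.

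The conclusion assumes that no separate document, such as the eCRF instructions, already requires outcome updates after exit. If one does, 11.3 contradicts it and should still be amended.

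**What to change.** Replace the last sentence of Protocol 11.3. SAEs (including SADEs and UADEs), events that led to withdrawal, and pregnancies open at exit should have outcome, seriousness and death updated in the eCRF until resolved or stable, or for a fixed period. Thirty days is one possibility, with pregnancies followed to outcome; that figure is illustrative and does not come from the documents.

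Add to 9.8 that withdrawal does not end this safety follow-up, subject to the subject's consent, and align the consent form. The withdrawal rules themselves need no change, and no contact is needed for subjects who exit without an open event of these kinds.

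The cost is protocol and eCRF wording, follow-up of what should be a small number of subjects, and a possible short delay to database lock for the last of them.

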11.4 Notification of Adverse Events

Sponsor Notification:

The investigational center staff must report all AEs to Medtronic in a timely manner. All severe hypoglycemia, DKA, HHS, SAE, SADE, and UADE should be reported as soon as possible (desired within 24 hours of investigator or study coordinator awareness) to Medtronic. For the previously mentioned events, the AE eCRF will be completed with all known details as soon as possible, this will serve as notification to Medtronic. If the study database cannot be accessed due to technical problems, contact the sponsor via email at [contact] and provide the de-identified known details of the event. Once the access issue has been corrected, the event should be entered onto an AE eCRF.

Source documents that support the event (e.g., clinic notes, hospital admission and discharge records, lab reports, EMT reports, ER/Urgent Care) should be provided upon request to the sponsor via Medtronic's secure upload application. All source documents/medical records should be redacted of patient identifiers (full name, address, etc.) prior to providing to the sponsor. Each source page should be identified with the subject ID.

11.5 Expedited Safety Reporting Requirements

For device studies, investigators are required to submit a report of a UADE to the sponsor and the reviewing IRB as soon as possible, but in no event later than 10 working days after the investigator first learns of the event (812.150(a)(1)). See **Section 12.20** for expedited reporting requirements for UADE.

The sponsor will notify the investigator and IRB of any event that results in a safety report per regulations to the FDA. Documentation of IRB notification of any safety event must be kept at the investigational center and a copy sent to the sponsor.

It is the responsibility of the investigator to follow their IRB reporting requirements.

11.6 Causality Assessment

An AE is not automatically related to the study device or procedure simply because the subject is wearing the device and participating in the study. The event should be reviewed to determine if the device or study procedure could have possibly caused the event and therefore is related to the study device or procedure.

Causality assessment is the determination of the relationship between an AE and the device being studied. It is expected that the investigational center will review all elements surrounding the AE to properly assess the causality of the event to the study device or to a study procedure.

This review would include the subjects' description of the event, study device uploads and medical records (if applicable) from the treating facility. These records will be made available to sponsor. Investigators should classify the relationship between the AE and the study device or study procedures using one of the four possible causality categories listed below:

- **Not related:** relationship to the device, comparator, or procedures can be excluded when:

- the event has no temporal relationship with the use of the investigational device or the procedures related to the application of the investigational device;
- the event does not follow a known response pattern to the medical device (if the response pattern is previously known) and is biologically implausible;
- the discontinuation of medical device application or the reduction of the level of activation/exposure – when clinically feasible – and reintroduction of its use (or increase of the level of activation/exposure), do not impact on the event;
- the event involves a body-site or an organ not expected to be affected by the device or procedure;
- the event can be attributed to another cause (e.g., an underlying or concurrent illness/ clinical condition, an effect of another device, drug, treatment or other risk factors);
- the event does not depend on a false result given by the investigational device used for diagnosis, when applicable;

In order to establish the non-relatedness, not all the criteria listed above might be met at the same time, depending on the type of device/procedures and the event.

- **Possible:** the relationship with the use of the investigational device, comparator, or the relationship with procedures, is weak but cannot be ruled out completely. Alternative causes are also possible (e.g., an underlying or concurrent illness/clinical condition or/and an effect of another device, drug or treatment). Cases where relatedness cannot be assessed, or no information has been obtained should also be classified as possible.
- **Probable:** the relationship with the use of the investigational device, comparator, or the relationship with procedures, seems relevant and/or the event cannot reasonably be explained by another cause.
- **Causal relationship:** the event is associated with the investigational device, comparator, or with procedures beyond reasonable doubt when:
 - the event is a known side effect of the product category the device belongs to or of similar devices and procedures;
 - the event has a temporal relationship with investigational device use/application or procedures;
 - the event involves a body-site or organ that
 - the investigational device or procedures are applied to;
 - the investigational device or procedures have an effect on;
 - the event follows a known response pattern to the medical device (if the response pattern is previously known);

- the discontinuation of medical device application (or reduction of the level of activation/exposure) and reintroduction of its use (or increase of the level of activation/exposure), impact on the event (when clinically feasible);
- other possible causes (e.g., an underlying or concurrent illness/clinical condition or/and an effect of another device, drug or treatment) have been adequately ruled out;
- harm to the subject is due to error in use;
- the event depends on a false result given by the investigational device used for diagnosis, when applicable;

In order to establish the relatedness, not all the criteria listed above might be met at the same time, depending on the type of device/procedures and the event.

Example: A severe hyperglycemia AE with the following event description would have the following causality assessment for device relatedness:

Improved glucose without an infusion set/site change	Not related
Changed infusion set with glucose improvement	Possible
Infusion set fell out, bent cannula, occlusion alarm	Causal relationship

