
 Remove a reservoir, without suspending and reconnecting after a while resulting in a hypoglycemia Patient not filling pump reservoir when needed leading to hyperglycemia Magnetic resonance imaging resulting in pump transmitter malfunction Inaccurate insulin delivery due to sudden altitude changes. Hypoglycemia or hyperglycemia from manual bolus Hypoglycemia or hyperglycemia from the use of the SmartGuard feature where SG values may be used to calculate insulin bolus amounts Hypoglycemia or hyperglycemia from computer hacking 	

Risks with hyperglycemia may include:
 
 Diabetic ketoacidosis or HHS Symptomatic ketosis Cardiovascular event Dehydration Potassium and sodium imbalance Shock Altered mental status Coma Acidosis 	
Prevention and mitigation include:
 
 Follow the provided user guides for insulin pump management. Train prior to study device use on appropriate device use and diabetes management principles and instruct to call investigator with problems. Instruct to check their meter glucose if their high symptoms do not match their sensor alerts or SG readings in order to make diabetes treatment decisions. Instruct to check their meter glucose if there are any concerns that the SG value is not accurate. Alternative method of managing glucose levels will be available (insulin and syringe for example).

Risks with hypoglycemia may include:
 
 Seizure Coma Altered mental status Loss of consciousness Cardiovascular event Death Risk of rebound hyperglycemia with ketosis 	
Prevention and mitigation include:
 
 Follow the provided user guides for insulin pump management. Train prior to study device use on appropriate device use and diabetes management principles and instruct to call investigator with problems. Instruct to check their meter glucose if their low symptoms do not match their sensor alerts or SG readings in order to make diabetes treatment decisions. Instruct to check their meter glucose if there are any concerns that the SG value is not accurate). Instruct to have glucose and glucagon on hand for hypoglycemia.
Risk with Sensors	Prevention and Mitigation

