
 • Hypoglycemia • Severe hypoglycemia • Hyperglycemia • Diabetic ketoacidosis or HHS • User entry error 
 ○ Patient administering boluses by entering false carb doses leading to hypoglycemia or hyperglycemia ○ Patient entering false glucose values for any reason leading to hypoglycemia and hyperglycemia ○ Patient entering false BG values for calibration leading to hypoglycemia or hyperglycemia • Sensor failure resulting from patient failure to calibrate leading to hypoglycemia or hyperglycemia • Sensor over-reading resulting in hypoglycemia • Sensor under-reading resulting in hyperglycemia • Sensor missed transmission, or any other fault resulting in no SG value, leading to hyperglycemia or hypoglycemia • Voluntary insulin delivery (with the pump or with a syringe) immediately prior to entering SmartGuard may result in severe hypoglycemia despite shutting down insulin delivery by the algorithm • Hypoglycemia related to patient taking insulin via injection while in Closed Loop (SmartGuard) • Hypoglycemia or hyperglycemia related to entering or exiting Closed Loop (SmartGuard) • Insulin over-delivery due to potential interference from acetaminophen • Cyber security hacking into pump 	
 • Instruct to avoid the use of products containing acetaminophen. • If acetaminophen is taken, subjects will be instructed to use additional BG meter readings to verify their glucose levels. • If acetaminophen is taken, while the SmartGuard feature is active, subjects will be instructed to use the temp target feature (when used, Auto Correction is not available). • Instruct subjects that in case of prolonged use of acetaminophen, the temp target feature can be used repeatedly and in succession. • Pump has cybersecurity encryptions to prevent hacking.

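### Row one of the causality example in Protocol 11.6 codes a severe hyperglycemia as not related on infusion-set evidence alone, against the section's own criteria

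*Protocol*

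**What the plan says.** Protocol 11.6 defines four causality categories. *Not related* applies when a relationship can be excluded, and one of its listed criteria is that "the event does not depend on a false result given by the investigational device used for diagnosis, when applicable". *Possible* covers a weak link that cannot be dismissed, and the section adds: "Cases where relatedness cannot be assessed, or no information has been obtained should also be classified as possible". Among the criteria for *Causal relationship* is that "the event depends on a false result given by the investigational device used for diagnosis, when applicable". The site is expected to look at everything surrounding the event, including the study device uploads.

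One worked example follows, introduced as: "A severe hyperglycemia AE with the following event description would have the following causality assessment for device relatedness". It has three rows:

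- Row one: "Improved glucose without an infusion set/site change" is coded Not related.
- Row two: improvement after the set was changed is coded Possible.
- Row three: an evident set problem (detached set, bent cannula or occlusion alarm) is coded Causal relationship.

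Protocol 11.2 takes the word device to cover any device used in the study. Table 4 in Protocol 10.1 names causes of hyperglycemia that do not involve the set: "Sensor under-reading resulting in hyperglycemia"; "Sensor missed transmission, or any other fault resulting in no SG value, leading to hyperglycemia or hypoglycemia"; moving into or out of closed loop; and "Hypoglycemia or hyperglycemia from the use of the SmartGuard feature where SG values may be used to calculate insulin bolus amounts".

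**The concern.** The example is the most concrete guidance that a site has when it codes a severe hyperglycemia, and it treats the infusion set as the only way in which the device can be at fault. A site that follows row one as written would code a sensor- or SmartGuard-caused event as Not related, although the definitions just above it would not allow that code.

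This matters most in Phase 2, which is meant to confirm the safety of the pump with a new sensor, the DS5. Table 1 lists the pump and the DS5 as investigational and the Extended infusion set as non-investigational. The example therefore asks about a non-investigational component and about neither investigational product. At stake is device attribution, not whether the event is recorded.

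**Working it through.** No plan figure needs reproducing and no rate can be computed: the documents give neither a severe hyperglycemia rate nor a split by cause. The check is a count and a side-by-side reading.

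**Count.**
- Rows in the example: 3. Rows that turn on the infusion set or site: 3. Rows that ask about sensor accuracy or about SmartGuard or pump delivery: 0.
- Table 4 routes to hyperglycemia through a sensor reading or SmartGuard: 3 under closed-loop therapy (under-reading; no sensor value; entering or exiting SmartGuard) + 1 under insulin administration and pumps (boluses based on sensor glucose) = 4. The failure-to-calibrate entry is left out because Protocol section 5 makes calibration optional.

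**Case A: sensor error.** The sensor under-reads, SmartGuard delivers too little insulin, and the subject meets the severe hyperglycemia definition. Glucose falls after a new sensor, a blood glucose entry or a manual correction, and the set is left in place.
- Row one gives Not related.
- The category definitions give at least Possible, because a device relationship has not been excluded. Dependence on a false sensor result would point further, towards Causal relationship.

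**Case B: recovery on injections.** Protocol Table 3 tells subjects to move from pump to injections if glucose stays above 300 mg/dL despite correction boluses and/or set changes. A subject who has tried boluses only, switches to injections and recovers also fits row one.
- Row one gives Not related.
- The definitions again give at least Possible. Improvement on stopping the device is one half of a listed causal criterion, the other half being the effect of reintroduction. Injections also bypass the set, so here even a set failure has not been cleared.

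**Where a wrong site code would travel.**
- *Clinical Events Committee (12.1).* Severe hyperglycemia is on its review list whatever the site's relatedness code. If it disagrees with the investigator, its adjudication is used for analysis.
- *Data Monitoring Committee (12.2).* It reviews the rate of device-related events. The documents do not say which code feeds that rate before adjudication, and the 10-business-day adjudication limit does not cover severe hyperglycemia. The committee also sees the all-cause severe hyperglycemia rate, which does not depend on the code.
- *Safety summary (Protocol 14.4.1.7, SAP 7.3.1.8).* SADE is listed and non-serious device effects are not, so only a serious event could change a summary line. Serious events also go to the Clinical Events Committee.
- *Anticipated or unanticipated (11.7).* This is assessed only for related events, but an event identified in the protocol counts as anticipated, and all four routes are in Table 4.
- *HbA1c change and time in range.* Neither uses the causality code.

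**The case against.** The strongest reply is that the rows are labelled an example, follow full definitions and do not override them. A site that reviews the uploads as 11.6 expects can reach the right code. Blood glucose evidence will usually exist, because the severe hyperglycemia definition itself requires a value above 300 mg/dL and subjects are told to test when symptoms and sensor disagree. The false-result criterion is qualified, and not every criterion need be met. The Clinical Events Committee has pump and CGM expertise, may draw on uploads and failure analysis, and has the last word for analysis.

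Most of this stands, and it limits the consequence. It does not remove the conflict. The introduction to the rows says what code such an event would have, and row one carries no condition, so following it literally gives a code that the definitions rule out. The conflict does not rest on the false-result criterion: the requirement that a relationship be excluded, and the default to Possible, are enough.

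A reader might go further and infer four things that the documents do not support:
- *That the final device-related results will be understated.* The committee reviews each of these events and its adjudication prevails.
- *That unanticipated device effects will be missed through 11.7.* The four routes are already in the protocol and would normally be anticipated. Only the reference to degree of incidence in the UADE definition, for serious events, leaves any room.
- *That the Clinical Events Committee will not consider the algorithm.* Item 1 in 12.1 does omit severe hyperglycemia from its algorithm question. However, item 2 names it and uses a software fault with under-delivery as its illustration, and item 4 leaves the causality factors open.
- *That completed Phase 1 events must be recoded.* Protocol 14.4 and SAP 7.3 evaluate the phases separately.

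**Conclusion.** The point holds as an internal contradiction in Protocol 11.6. For a severe hyperglycemia caused by the sensor, by loss of sensor glucose, or by SmartGuard or pump delivery, row one gives Not related where the section's criteria give at least Possible.

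Its reach is narrow: the site's initial device attribution, the Data Monitoring Committee's device-related event rate (mainly before adjudication), and any SADE classification of a serious event. The all-cause severe hyperglycemia incidence and the primary and secondary endpoints are unchanged. The number of events concerned is unknown and cannot be bounded from the documents. The conclusion assumes only that some sites will apply the example as it is worded.

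**What to change.** Reword row one of the example in Protocol 11.6 so that it reads: "Improved glucose without an infusion set/site change", and device uploads and blood glucose exclude sensor error and SmartGuard or pump delivery as a cause: Not related; otherwise Possible.

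The cost is one line of text and a few more events coded Possible. The upload review that it calls for is already expected of sites. Adding severe hyperglycemia to the algorithm question in 12.1 item 1 is optional. Phase 1 events need re-review only if device-related rates are to be compared between phases.
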